#### **II.E. Response Rates, Missing Values and Data Imputation on the Survey Data Collection Datasets**

Response rates for the main data collection will be calculated using AAPOR response rate formula 4 (RR4). This formula includes both complete and partial completed surveys/interviews for inclusion in the numerator and allocates cases of unknown eligibility in the denominator. This is particularly important given that the phone number data may be incomplete, incorrect, or phone numbers may be disconnected and we therefore may not be able to know the eligibility of the case. We will examine survey refusals and nonresponse to determine if there is the potential for nonresponse bias based on certain patient subgroups and/or hospital subgroups and make corrections if possible.

For item nonresponse, we will examine if certain items have higher missing data than others. Given that the patient surveys will be designed to assess experiences with care, if the respondent does not indicate that they experienced a specific care component, we will not impute data on their experience with it.

#### **II.F. Analysis of Patient Survey Datasets**

**Psychometric analysis.** Westat will compile patient survey data from the main study, conduct data cleaning, and generate descriptive statistics from the survey results. Psychometric analyses will be conducted to examine items for variability of response, missing percentages, calculate reliability statistics, perform confirmatory factor analysis to examine the factor structure of the measures, and examine inter-correlations of items and composites. Final composite scores will be created and the survey data will then be used to examine the study's aims and hypotheses regarding TC delivery and outcomes.

**Descriptive statistics.** Continuous variables will be summarized with descriptive statistics (n, mean, standard deviation, median, quintiles, and min and max); categorical variables will be described with counts and percentages. All data will be unweighted. For each survey type

(i.e., patient, caregiver, provider), numerical and/or graphical summaries will be provided overall and by subpopulations.

**II.G. Analysis of TC Component Exposure.** Analyses will be conducted using both hospital- and patient/caregiver-level data. Comparisons on outcomes will be made first using TCCs identified by the hospital; additional analyses will use patient/caregiver identified components. Moreover, additional analyses will also use the number and occurrence of specific categories received within a component as a measure of the TCC received. Finally, an additional issue for consideration is that indicators for TCC presence or absence may not be sufficient for identifying TC component “exposure.” It is expected that TCCs in different communities/hospitals will be implemented to varying degrees. Non-uniform implementation may provide a natural experiment where communities/hospitals serve as their own control and the longitudinal effects of the TC component can be investigated. Using process and implementation data collected at Phase 2, segmented regression analysis of interrupted time series data will allow for comparisons and the estimation of effects for different intensities of TC component exposure.

Although every effort will be made to include the possible combinations of TC components, it is unlikely that all combinations will be present in each subpopulation. Additionally, although many TC component factors will be measured, it is not expected that all of them will impact the outcomes (sparsity of effects). As an alternative to the factorial design utilized in an experiment, fractional factorials may also be utilized, where a large number of factors can be “screened” to detect important factors even in the presence of a small number of hospitals.

As an additional visualization tool, tree-based models (CART and Random Forests) may also be used to identify potential higher-order interactions. Although the primary analysis will be conducted within a subpopulation, exploratory analyses will be used to investigate the interaction of subpopulation characteristics, patient/caregiver characteristics, and TC components on outcomes. The identification of these potential combinations will help inform additional comparative analyses in the presence of a large number of potentially correlated variables.

- **Pooled Analysis**

Based on the statistical power available with a survey response rate of 35 percent, we conclude that the resulting sample size of approximately 9000 patients from 46 hospitals represents the minimum sample required to ensure that the ACHIEVE prospective analysis can detect the comparative effects of transitional care strategies on important patient outcomes of interest. Our power analysis is based on the study’s ability to detect meaningful differences in outcomes across groups of hospitals that implement different combinations of transitional care (TC) components. Results from the ACHIEVE survey pilot test indicate that the patient survey response rate could be as low as 35 percent. To assess the impact of this response rate on statistical power, we conducted a Monte Carlo simulation using data from the ACHIEVE retrospective analysis, which includes Medicare claims data from nearly 400 hospitals and all Medicare patients hospitalized at these facilities

over five years. This simulation allowed us to assess the likely statistical power of the prospective analysis even though we do not yet know with certainty the distribution of TC components and patients across participating hospitals. This simulation assumes that the distribution of TC components and patients among hospitals recruited for the ACHIEVE prospective study will be consistent with the distributions observed in the larger population of hospitals included in the ACHIEVE retrospective study.

We conducted the simulation as follows: (1) we drew a random sample of 46 hospitals from the nearly 400 hospitals included in the ACHIEVE retrospective data; (2) we drew a random sample of 560 patients from each of the 46 selected hospitals, corresponding with the planned data collection period of 28 weeks and the planned recruitment rate of 20 patients per week at each facility; (3) we drew a random sample of 35 percent of the recruited patients at each hospital, corresponding with the assumed minimum response rate; (4) we used the 5 clusters of TC components identified from the ACHIEVE retrospective analysis to classify hospitals into comparison groups based on which TC components they implemented for their patients; and (5) we used a multivariable logistic regression model to estimate minimum detectable differences (using a 5% significance level) in 30-day all-cause readmission rates across hospitals grouped by TC clusters, while controlling for patient characteristics that may impact readmission (e.g., age, race, sex, comorbidities, and dual eligible status, as well as others), and accounting for patient clustering within hospitals. We used 1000 replications of this simulation to estimate the variances in minimum detectable differences.

Simulation results indicate that at an average patient response rate of 35 percent, the study will have sufficient power to detect differences in readmission rates of 2.1 to 2.9 percentage-points across the TC clusters at  $p=0.05$ . This level of statistical power will allow the study to detect effect sizes that are somewhat smaller than the effects estimated from prior studies of care transition interventions, such as the 3.6 percentage-point reduction in readmissions observed in Eric Coleman’s care transition intervention trial. Because the ACHIEVE analysis compares outcomes across multiple active treatment groups defined by TC clusters—rather than comparisons between a single treatment group and control group—and because readmission rates have been declining nationally since 2012, it is important for the ACHIEVE study to be powered to detect somewhat smaller effect sizes than those found in previous two-group studies. For this reason, we consider a response rate of 35 percent to be the minimum acceptable response rate for the ACHIEVE prospective study. This would be approximately 9000 patients.

- **Subgroup Analysis**

Several patient subgroups and community settings are of special interest in the ACHIEVE analysis, including patients with multiple comorbidities, dual eligibles, low-literacy populations, and rural communities. It is not possible to estimate minimum sample sizes for subgroup analysis with any reasonable level of precision given the lack of a priori information about how patient covariates and TC clusters

are distributed within and across these subgroups. Our simulation analyses suggest that the minimum effect sizes we will be able to detect for subgroups could be more than two times larger than the 2.1 to 2.9 percentage points estimated for the pooled analysis as a whole, when using traditional multivariable analysis methods. For this reason, we anticipate using a modified analytical approach that relies on Bayesian estimation methods that borrow statistical power from the full ACHIEVE sample in order to support statistical inferences about subgroup differences. This method has been used successfully in several recent federal studies of similar magnitude and scope, including the 2016 Mathematica Policy Research evaluation of the CMS Comprehensive Primary Care Initiative. The primary limitation of Bayesian estimation with small subgroup sample sizes is that results can be sensitive to incorrect assumptions about the prior probability distributions of the effect sizes. A major strength of the ACHIEVE study is that we can use estimated effects from the ACHIEVE retrospective analysis to specify informative prior probability distributions for the effect sizes to be estimated in the prospective analysis, rather than basing these distributions on uninformed assumptions.

[figure not shown]
- **Limitations of the Simulation Analysis**

Our simulated power analyses use retrospective Medicare claims data from 2013-14 and are based upon relatively limited a priori knowledge about the TC components implemented by individual hospitals and self-reported by hospital staff. In particular, the measures of TC components are hospital-level measures and do not account for within-hospital differences in the implementation of TC components for individual patients. The ACHIEVE prospective study will collect much more detailed, patient-level information about the TC components received by individual patients, as reported by patients and caregivers. These enhanced, patient-level measures of TC exposure will further improve the study's statistical power to detect differences in outcomes attributable to TC components. As such, this power analysis provides conservative, lower-bound estimates of minimum detectable differences.

[figure not shown]
**Inferential Analysis.** Utilizing the information from fractional factorials and tree-based approaches, hierarchical models will be used to compare TC component exposures while accounting for hospital-level characteristics, patient characteristics, and community demographics. Both GEEs and GLMMs (with random intercepts and coefficients) will be used to examine the relationship of TC component exposure using hierarchical characteristics of the community-hospital-patient triad.

[figure not shown]

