## **Project ACHIEVE Analytic Plan – Study Protocol, Updated on December 20, 2017**

### **II. Prospective Analysis, Patient survey**

The prospective analysis will use detailed measures collected directly from patients about the types of TC components they receive and experience during care episodes. This analysis will define and classify TC clusters (comparators) on a much more granular level. However, to maximize the study's power to detect the individual and combined effects of TC components and to realize efficiencies in primary data collection, a Fractional Factorial (FF) design will be used to select fractions (subgroups) of the TC clusters and care settings in which to collect detailed, prospective patient data.

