### **II.C. Study Outcome Measures**

***Patient utilization of health services*** include 30-day ED visits, 30-day rehospitalizations

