### **II.D. Development and Validation of the Patient Survey Instruments**

Westat will develop a draft survey instruments consisting of items designed to elicit patient experiences with the delivery and receipt of TC components, as well as patient-reported outcomes relevant to transitions in care.

Draft items will be derived from TC measurement constructs identified from an updated literature review, existing validated instruments such as the Coleman CAHPS Care Transition questions, items listed in the NIH PROMIS repository, and constructs elicited from focus groups and hospital site visits. Draft instruments will be refined based on at least two cycles of iterative review by members of the ACHIEVE study team, including members with relevant clinical expertise, TC program development and implementation expertise, and patient and caregiver experience.

Once draft items have been developed, cognitive interviews will be conducted to examine item clarity, comprehension, difficulty, and face validity. Cognitive interviews will be conducted with up to 14 participants in two iterative rounds. The patient survey will also be translated into Spanish and up to 6 cognitive interviews will be conducted to pretest the translated items. The surveys will be revised as needed based on feedback from the cognitive interviews, in preparation for pilot testing.

Significant changes were required in the administration of the patient and caregiver survey component of Project ACHIEVE based on uncovering potential conflict with CMS HCAHPS. Numerous follow-up conversations with CMS, HSAG, PCORI and the ACHIEVE research team yielded agreement on Project ACHIEVE being allowed to field its patient survey 51 days after patient hospital discharge; after most patients contacted for HCAHPS have completed their survey and without causing significant disruption to hospitals' participation in HCAHPS. Of note, we originally proposed to call patients between 30 and 45 days post discharge.

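### In the additional analyses of II.G, a 30-day readmission can itself change the patient-reported exposure, and the plan states no safeguard

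*Combined protocol and SAP*

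**What the plan says.** Section II presents the prospective study as resting on "detailed measures collected directly from patients about the types of TC components they receive and experience during care episodes". Section II.G sets the order of analysis: "Comparisons on outcomes will be made first using TCCs identified by the hospital; additional analyses will use patient/caregiver identified components". It then adds that "additional analyses will also use the number and occurrence of specific categories received within a component", so counts also serve as exposures.

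The utilization outcomes in II.C "include 30-day ED visits, 30-day rehospitalizations". Section II.D records the agreement to "field its patient survey 51 days after patient hospital discharge"; the earlier proposal was to call between 30 and 45 days. Footnote a of the flow chart confirms that survey responses are linked to utilization data.

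The Inferential Analysis paragraph plans GEEs and GLMMs that adjust for hospital, patient and community characteristics. The stated data checks are of three kinds:

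- In II.D, "cognitive interviews will be conducted to examine item clarity, comprehension, difficulty, and face validity".
- In II.E, the team will "examine survey refusals and nonresponse to determine if there is the potential for nonresponse bias based on certain patient subgroups" and look at item missingness.
- In II.F, variability, reliability and factor structure are examined.

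**The concern.** In the additional analyses the exposure is recorded after the outcome, by people who have already had it or escaped it. The outcome can then shape the exposure in two ways.

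- **Truncation.** A patient readmitted in the first days may never receive a service due later after discharge. Non-receipt is then a result of readmission, and the component looks protective. This does not depend on when the survey is fielded.
- **Second-stay reporting.** A readmitted patient asked after day 30 may report care given around the second stay. The component then looks harmful.

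Baseline adjustment handles common causes of exposure and outcome. It does not remove a path from outcome to exposure. None of the stated checks compares reported exposure by 30-day event status or separates components by timing.

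Patient-level exposure is what the prospective study is meant to add, and the discussion of simulation limitations in II.G presents it only as a gain in power. With about 9,000 patients, a small reporting gap can reach significance and be read as a component effect.

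**Working it through.** **Order of events.** The outcome window closes at day 30 and the survey starts at day 51, so 51 − 30 = 21 days separate them. Every counted readmission precedes the patient's report. The earlier 30–45 day proposal would also have fallen at or after the end of the window.

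**The plan's own sample size.** 28 weeks × 20 patients = 560 per hospital; 560 × 0.35 = 196 responders; 46 × 196 = 9,016. This reproduces the stated figure of about 9000.

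**The plan's detectable difference.** The plan states power for "differences in readmission rates of 2.1 to 2.9 percentage-points across the TC clusters". Base rate, intraclass correlation, cluster sizes and power level are not given, so the figure cannot be reproduced exactly. A two-proportion approximation without clustering (assumed 15% base rate, 80% power, two-sided 5%) gives 2.1 points for two halves, 2.6 for one fifth against the rest, and 3.3 for one fifth against another. The order of magnitude is plausible. It concerns hospital clusters, so it serves here only as a yardstick.

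**Spurious difference under no true effect.** Let p be the readmission rate, e reported receipt among patients not readmitted, and e + d among those readmitted. By Bayes' rule the apparent difference is

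p(e+d)/[p(e+d) + (1−p)e] − p(1−e−d)/[p(1−e−d) + (1−p)(1−e)].

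The documents give none of p, e or d. Assume p = 0.16 and e = 0.50.

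- d = 2 points: 0.0832/0.5032 − 0.0768/0.4968 = 0.1653 − 0.1546 = 1.08 points.
- d = 5 points: 0.0880/0.5080 − 0.0720/0.4920 = 0.1732 − 0.1463 = 2.69 points.
- The d needed for a spurious 2.1 points is 3.9 points. It runs from 2.7 to 5.0 points over readmission of 12–20% and prevalence of 30–70%.

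**False positives.** Simulation of 46 hospitals × 196 patients used assumed hospital SDs of 0.2 (readmission logit) and 0.5 (exposure logit). The analysis was a within-hospital regression with hospital-clustered standard errors, over 3,000 replications with no true effect. Rejection at a nominal 5%:

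| Net gap d | 16% readmission | 12% to 20% readmission |
|---|---|---|
| 0 | 4.5% | – |
| 2 points | 30.0% | 23.7% to 32.9% |
| 5 points | 94.8% | 87.4% to 96.7% |

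A separate simulation of independent patients at 10–20% readmission gave 21–33% for 2 points and 82–97% for 5 points.

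**How such gaps could arise.** Assume that readmission time is uniform on 0–30 days and the post-discharge contact is uniform on 0–w days. Readmission then precedes contact with probability w/60. For w = 7, receipt among readmitted patients is 0.5 × (1 − 7/60) = 0.442, a gap of −5.8 points. For w = 3 it is 0.475, a gap of −2.5 points.

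If a share f of readmitted patients also counts a second stay with 50% receipt, receipt becomes b + f(1 − b) × 0.5, where b is the truncated value. With w = 3 and f = 0.1 this is 0.475 + 0.1 × 0.525 × 0.5 = 0.501, and the two mechanisms nearly cancel. With w = 14 and f = 0.1, b = 0.383, receipt is 0.414, the gap is −8.6 points and the apparent difference is −4.6 points. The net bias can therefore be negligible or large, and of either sign.

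The figures are for rehospitalization; ED visits were not quantified.

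**The case against.** The strongest reply has four parts.

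1. **The plan already puts the safer exposure first.** Hospital-identified components lead, and the patient-reported analyses are labelled additional. II.G also plans segmented regression on process and implementation data, with communities or hospitals as their own controls, which offers triangulation. This stands. A reader might infer that the study's leading comparisons are biased; the documents do not support that, since those comparisons do not rest on patient report. Neither route, however, repairs the patient-level analyses.
2. **The instrument is unseen.** Items may be anchored to the index stay, which would limit second-stay reporting. This also stands. Anchoring cannot remove truncation of a post-discharge component, because there the report of non-receipt is accurate.
3. **Every bias input is assumed.** This is right. The figures show how sensitive the analysis would be to a gap, not that a gap exists. A reader might infer that bias has occurred or has a known direction; nothing in the documents shows either.
4. **Tabulating receipt by event status is no test.** It is the same association read in reverse. At 16% readmission and about 50% prevalence, a genuine −3-point effect and a pure artefact of −3 points both show a 5.6-point gap. This is correct, so such a display can only serve as a tipping-point analysis.

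It is also tempting to label every patient-reported utilization analysis exploratory. That goes too far: pre-discharge items are not open to truncation and, if anchored to the index stay, should not be open to second-stay reporting.

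**Conclusion.** The point holds for the additional analyses only, and should be fixed. As II.G is written, reported receipt of any component delivered after index discharge would be related to an outcome that can prevent that receipt. Neither the planned models nor the stated checks deal with this. Second-stay reporting is a further possibility that depends on item wording that cannot be seen.

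Size and sign are unknown. Under the assumed inputs, a net reporting gap of 2 to 5 points would give a spurious difference of 1.1 to 2.7 points. Its upper end is comparable with the 2.1 to 2.9 points that the plan treats as detectable across hospital clusters. Confidence is medium: the order of events and the silence of the text are certain, but the inputs are assumptions, and the supplied text does not show which items cover post-discharge care.

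**What to change.** Add to II.G:

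> Each survey item is marked as delivered before or after index discharge, and its reference period (index stay or not) is stated. For 30-day utilization outcomes, results are reported separately for the two sets. Results for post-discharge components, and for counts that include them, are flagged as open to reverse causation and are not interpreted as effects of the component. As a sensitivity (tipping-point) analysis, not a test for bias, we report how large a difference in reporting by 30-day event status would remove each association.

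The item marking isolates the set open to truncation, and the stated reference period shows which items are open to second-stay reporting. The tipping-point figure lets readers judge each result against the gap that they find plausible.

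The cost is a one-time item list and a little more analysis. No new data and no exclusions are needed. The downside is more cautious conclusions for post-discharge components.

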#### **II.B. Selection of Factors and Levels for Prospective Data Collection**

The sampling frame for the prospective FF design includes the full range of TC clusters along with the full range of hospital and community settings and patient subgroups in which these clusters are implemented. Results from the retrospective analysis will be used together with results from the hospital site visits and responses of Organizational TC Implementation Assessment (OTCIA) form to identify which combinations of TC clusters, care settings, and patient subgroups are most important to study in detail. A FF design matrix will be

constructed that lists all TC components and all important organizational, community, and patient characteristics as possible factors and interactions. The organizational, community and patient characteristics to include in the matrix will be based on the retrospective analysis results showing which cluster/setting/patient interactions achieved significant improvements in outcomes. Results from the OTCIA will be used to determine which cells can be dropped from the design matrix altogether (given zero weight) because the specific TC cluster/setting/patient combination does not exist in practice. Other cells will be assigned increased weight because they include clusters that are highly valued by patients and caregivers, or because the retrospective analysis shows that the cell is associated with improved outcomes. From this design matrix, a subset of comparators will be selected that maximize the study's ability to detect unconfounded main effects and interaction effects involving TC components, care settings, and patient subgroups.

Based on our team's existing knowledge of and experience with the organized TC programs and their TC components, we anticipate that it will be necessary to include at least 6 TC clusters in the prospective FF design with approximately 5 hospitals per cluster in order to adequately characterize the existing heterogeneity in TC program implementation, care settings, and patient subgroups (Figure 1). The exact number of clusters and hospitals per cluster will be determined by analysis of the FF design matrix. Surveys will be fielded with a total of 46 hospitals and an average of 300 patients per hospital.

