In the event that an insufficient number of TC/setting/patient combinations are available to utilize the fractional factorial design for a subpopulation, ***data visualization*** will be used to identify potential comparators for ad-hoc analyses and descriptions. This more ad-hoc approach has potential analytical issues if one hospital contributes a significant portion of the patients for a subpopulation, and separating the TCC/cluster from the hospital-effect may be difficult. Therefore, in the selection of hospitals, availability of subpopulations and presence of particular TCs will be carefully considered; obtaining a sample of hospitals based on TCs *and* needed combinations of subpopulations per the fractional factorial design will avoid the potential for analyzing and describing patients within a single hospital.

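### The analysis called primary is within an unnamed subpopulation, but the 9,000-patient size and the 2.1 to 2.9 point detectable differences were derived only for the pooled comparison

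*Combined protocol and SAP*

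**What the plan says.** All of this is in the combined protocol and SAP, section II.G and the blocks that follow it.

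- **Which analysis is primary.** In the paragraph on tree-based models, II.G states: "Although the primary analysis will be conducted within a subpopulation, exploratory analyses will be used to investigate the interaction of subpopulation characteristics". The sentence goes on to patient and caregiver characteristics and TC components. It does not say which subpopulation is meant.
- **What was sized.** The Pooled Analysis block, directly below, gives 46 hospitals and roughly 9,000 patients and says that this total "represents the minimum sample required to ensure that the ACHIEVE prospective analysis can detect the comparative effects of transitional care strategies". The supporting simulation samples patients at each hospital without regard to subgroup and estimates minimum detectable differences "in 30-day all-cause readmission rates across hospitals grouped by TC clusters". The result is 2.1 to 2.9 percentage points. The plan compares this with effects from earlier studies, "such as the 3.6 percentage-point reduction in readmissions observed" in a trial of a care transition intervention.
- **What is said of subgroups.** The Subgroup Analysis block states: "It is not possible to estimate minimum sample sizes for subgroup analysis with any reasonable level of precision". It adds that, with traditional multivariable methods, the smallest detectable effects "could be more than two times larger than the 2.1 to 2.9 percentage points estimated for the pooled analysis as a whole". For that reason it anticipates a Bayesian approach that draws strength from the whole sample, with informative priors from the retrospective analysis. It warns that wrong priors can influence the results.
- **Which models are listed.** The readable text of Inferential Analysis names hierarchical models, GEEs and GLMMs with random intercepts and coefficients. It mentions neither subpopulations nor Bayesian estimation.

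**The concern.** A sample-size claim belongs to one analysis. Here it is attached to the pooled comparison, while the word *primary* is attached to something within a subpopulation. No readable sentence makes the pooled comparison primary, and none names the primary subpopulation.

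Two things are at stake. First, if the clause means what it says, the subgroup limitation that the plan discloses applies to its main result, and the assurance given for 9,000 patients does not cover that result. Secondly, while the choice stays open, the pooled result or any one subpopulation result could be presented as primary after the data are seen.

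The remedy that the plan offers for weak subgroup precision is borrowing. It is only anticipated, and the section that lists the inferential models does not take it up.

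**Working it through.** **Inputs**, all from the Pooled Analysis and Subgroup Analysis blocks:

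- 46 hospitals; 28 weeks × 20 patients per week = 560 recruited per hospital; 35% response.
- 5 TC clusters; 5% significance level (sidedness not stated; two-sided assumed below).
- Pooled detectable differences of 2.1 to 2.9 points; no power level stated.
- Benchmark of 3.6 points; subgroup inflation that could exceed a factor of 2.

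**Step 1: reproduce the stated size.** 46 × 560 × 0.35 = 9,016, against about 9,000 stated (0.2% apart). No simulation step restricts patients to a subgroup, so this is the pooled sample. The 2.1 to 2.9 points cannot be reproduced, because the readable text gives no power level, baseline readmission rate, intracluster correlation or number of hospitals per cluster. They are taken as stated.

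**Step 2: apply the plan's own inflation.** 2 × 2.1 = 4.2 and 2 × 2.9 = 5.8 points. Since the plan speaks of more than a doubling, these are the lower edge of that statement.

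**Step 3: compare with the benchmark.** To stay at or below 3.6 points, a subgroup can tolerate inflation of at most 3.6/2.1 = 1.71 or 3.6/2.9 = 1.24. Both are below 2.

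As a rough guide, assume that the detectable difference scales as 1/√(share of sample). A doubling then corresponds to a share of 1/2² = 25%, or 9,016/4 = 2,254 patients. Staying at 3.6 points needs a share of (2.1/3.6)² = 34% to (2.9/3.6)² = 65%. This scaling ignores clustering. A subgroup spread over the same hospitals loses somewhat less, because fewer patients per hospital lower the design effect. The readable text gives no subgroup shares.

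**Step 4: illustration of power for 3.6 points.** Power = Φ(3.6 × k/M − 1.96), where M is the detectable difference and k = 1.96 + 0.842 = 2.802 if M refers to 80% power, or 1.96 + 1.282 = 3.242 if 90%. For example, with M = 4.2 and k = 2.802: 3.6 × 2.802/4.2 − 1.96 = 0.442, and Φ(0.442) = 67%.

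| M (points) | Basis | If M is at 80% power | If M is at 90% power |
|---|---|---|---|
| 2.1 | pooled | 99.8% | >99.9% |
| 2.9 | pooled | 94% | 98% |
| 4.2 | exactly doubled | 67% | 79% |
| 5.8 | exactly doubled | 41% | 52% |

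The 80% and 90% conventions are assumptions, and the doubled rows apply to traditional methods only.

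**Step 5: compare the methods.** Subgroup Analysis anticipates Bayesian estimation using the whole sample. Inferential Analysis lists GEEs and GLMMs. A GLMM with random coefficients could be fitted as a partially pooled Bayesian model, but the readable text does not say that it will be. If each subpopulation were fitted separately, the other patients would contribute nothing, and only the retrospective priors would add information.

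**The case against.** The strongest reply is that this is one subordinate clause in a paragraph about exploratory tools. All the sizing work treats the pooled comparison as the main one and brings in subgroups afterwards as of special interest. The plan is also candid: the 9,000 figure stands under a pooled heading, and the next block gives the subgroup limits and a method to ease them. The plan adds that patient-level exposure measures should improve power.

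Much of this stands. The clause may be loose wording, and the disclosure is real. Disclosure does not settle which analysis is primary, however. Nor is the clause wholly isolated, since II.B provides for the case in which an "insufficient number of TC/setting/patient combinations are available to utilize the fractional factorial design for a subpopulation". That text concerns feasibility and does not use the word primary, so it is only weak support. The claimed gain from patient-level exposure is not quantified and does not bear on which analysis is primary.

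A reader might infer more than the documents support:

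- *That II.B contradicts II.G on interactions.* II.B aims to maximise the study's "ability to detect unconfounded main effects and interaction effects involving TC components, care settings, and patient subgroups". That is an aim for sampling cells. A design can support interactions without making each one confirmatory, and the II.G sentence can be read as concerning multi-way interactions.
- *That a primary analysis within a subpopulation rules out borrowing.* II.G does not say that models will be fitted to each subpopulation alone. A subpopulation effect can be estimated from a full-sample model.
- *That the power percentages measure a shortfall.* They assume a power convention and a method that the plan moves away from for subgroups. No text sets 3.6 points as a subgroup target.
- *That the exclusion counts in the flow-chart notes show that outcomes were analysed before the priors were set.* They show only that records were processed.

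**Conclusion.** The point holds: the stated size and detectable differences belong to a different analysis from the one called primary. On the plan's own figures, a subgroup under traditional methods could need more than 4.2 to 5.8 points, above the 3.6-point benchmark used for the pooled comparison. The plan says *could be*, and large subgroups may do better. The borrowing meant to offset this is not carried into the readable list of inferential models.

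This should be fixed, but it does not show that the study is too small. If the pooled comparison is what the sponsor means by primary, correcting the clause removes the mismatch in size, and the modelling gap remains. Confidence is medium. The conclusion rests on readable text, and figures that follow the subgroup, limitations and inferential blocks are not shown. The doubling is the plan's own statement; the power percentages are illustrations only.

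**What to change.** 1. **II.G, the clause on the primary analysis.** Choose one of two wordings; the choice is the sponsor's. Either make the pooled TC-cluster comparison primary and within-subpopulation results secondary, or keep subpopulations primary, name them, and state that 9,000 patients and 2.1 to 2.9 points do not apply to them.
2. **Subgroup Analysis and Inferential Analysis.** State that subpopulation effects will be estimated from the full-sample borrowing model already anticipated, and not from separate fits within each subpopulation. Limit this to combinations of TC exposure and subpopulation present in enough hospitals to be estimable, since II.G expects some combinations to be absent.
3. **Priors.** Set the retrospective-based priors before prospective outcomes are analysed, or disclose that this was not done. Add one sensitivity analysis with a weakly informative prior, because the plan itself warns of sensitivity to the prior.

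The cost is revised wording, a written model specification and one further analysis; no new data are collected. The drawbacks are shrinkage of subgroup estimates and, if subpopulations stay primary, a less favourable statement of what 9,000 patients can support.
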